9. CORRELATIVE / SPECIAL STUDIES/ LABS

- 9.1. B-hydroxybutyrate: It is necessary to obtain measures of ketone bodies to determine that the diet is producing the desired biological effect. In addition, this is one method to assess patient compliance. Serum BHB is a quantitative measure of ketosis that is less dependent on hydration status than other measures. In addition, the level of serum ketosis will be correlated with treatment outcome. It is speculative if the level of

ketosis as based on low, moderate or high will correlate with the treatment outcomes of treatment response, PFS 6 and overall survival.

9.2. Blood glucose: Measurement of blood glucose is necessary in patients on a low carbohydrate diet in order to monitor for hypoglycemia (< 70mg/L) for patient safety. In addition, serum glucose is known to be a prognostic factor for survival in GBM. The level of blood glucose will be correlated with treatment outcome. Every attempt will be made to obtain glucose levels fasting.

9.3. Blood insulin: Insulin is expected to be inversely related to beta-hydroxybutyrate. Insulin also will be important to measure, as reductions of insulin, a proliferative hormone, may be important mechanistically in the benefit associated with the nutritional intervention. Further, in our preliminary studies with older adults with MCI, insulin level was inversely related to cognitive performance. Insulin levels have been important in in IGF-1 pathway and therefore are important in addition to the fasting glucose levels. Every attempt will be made to obtain insulin levels fasting.

9.4. Complete Metabolic Panel: This is already monitored weekly for treatment of gliomas with temozolomide and radiation. However will be important to monitor for hyponatremia and increased creatinine indicating dehydration. CO₂ will also be measured on this test and will determine if lactate levels need to be drawn to check for acidosis.

9.5. Imaging: MRI tumor imaging will be performed before radiation as a pre-planning scan, and 4 weeks after completion of radiation. Then MRI's will be done as per treating physician recommendations. The treatment planning MRI will occur as clinically ordered. The prior diagnostic MRI examination with contrast and the concurrent imaging for treatment planning will be employed in selecting the two locations. For the two locations, we will interrogate a) the solid portion of the tumor and b) a control region without tumor, preferably within the thalamus (left hemisphere preference; right hemisphere if tumor involvement within the left).

9.6. Neurocognitive Assessment: We will administer measures of attention, working memory, long-term memory, speed of processing, depression and anxiety prior to initiation of intervention and at termination of intervention. This is to determine effect of intervention on cognition and mood.

9.7. Peripheral Platelet Mitochondrial function: Whole blood will be obtained pre-treatment visit #2, post-treatment visit #1 and post-treatment visit #2. Patients are already having blood drawn at these visits as standard of care. This sample will be transported within hours to the laboratory of **[name] at Cincinnati Children's Hospital Medical Center** for assessment of mitochondrial respiration in the platelets. Our preliminary data has shown that this measure responds to the institution of nutritional ketosis, and we would expect to observe enhanced state III respiration and uncoupling at termination of the intervention

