 - 3.2.4. Neurocognitive testing will be performed at the pre-treatment visit #2, at the post-treatment visit #1 and then at post-treatment visit #2
- 3.3. **Number of Participants:** Thirty evaluable patients will be enrolled. Because this is a feasibility study, ECOG performance status and MGMT methylation which are both predictors of survival will be recorded but not used for stratification.

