4. PATIENT SELECTION

4.1. Inclusion Criteria

- 4.1.1. Patients must have a histologically confirmed primary malignant glioma (Grade III (1p/19q intact) or Grade IV tumor). Patients can have a radiographically confirmed diagnosis if biopsy is not possible, but this must be approved by the primary investigator.

- 4.1.2. No uncontrolled infection or other active malignancy or chronic systemic immune therapy.
- 4.1.3. Age ≥ 18 years.
- 4.1.4. ECOG performance status ≤ 3 (see Appendix A).
- 4.1.5. Life expectancy $>$ three months.
- 4.1.6. Ability to understand and willingness to sign a written informed consent document.
- 4.1.7. Patients can be on an investigational study but will not be eligible if the investigational drug is given during the intervention
- 4.1.8. Physician must have the intent to treat with the Stupp Protocol.
(<http://www.nejm.org/doi/full/10.1056/NEJMoa043330>)
- 4.1.9. Patient must be on steroid dose of dexamethasone ≤ 8 mg at study entry.
- 4.1.10. Adequate renal function, defined as follows: Serum creatinine \leq institutional ULN within 14 days prior to registration. Creatinine clearance (CC) ≥ 60 ml/min within 14 days prior to registration determined by 24- hour collection or estimated by Cockcroft-Gault formula: CC_{Cr} male = [(140 – age) x (wt in kg)] [(Serum Cr mg/dl) x (72)]; CC_{Cr} female = 0.85 x (CrCl male)
- 4.1.11. Adequate hepatic function defined as follows: Total bilirubin $< 2 \times$ institutional ULN within 14 days prior to registration; AST or ALT $< 3 \times$ institutional ULN within 14 days prior to registration.

4.2. Exclusion Criteria: The presence of any of the following will exclude a patient from study enrollment.

- 4.2.1. Patients who are pregnant
- 4.2.2. Patients with a genetic disorder of fat metabolism.
- 4.2.3. Patients with IDDM or Type 2 diabetes diagnosed with a hemoglobin A1C > 6.4
- 4.2.4. Patients who are allergic to dairy or lactose intolerance
- 4.2.5. Patients with known inborn errors of metabolism of primary carnitine deficiency, carnitine palmitoyltransferase I or II deficiency, carnitine translocase deficiency, beta-oxidation defects, pyruvate carboxylase deficiency and porphyria.
- 4.2.6. Patients with pancreatic insufficiency or history of pancreatitis within last 5 years
- 4.2.7. Patients with gallbladder dysfunction or disease
- 4.2.8. Decompensated congestive heart failure

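### The planned correlations of BHB and glucose with outcome name no adjustment for baseline ECOG, so fitness to keep the diet can make ketosis look beneficial when it is not.

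*Combined protocol and SAP*

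**What the plan says.** Section 9.1 commits to an analysis of BHB against outcome: "the level of serum ketosis will be correlated with treatment outcome". It then calls it speculative whether "ketosis as based on low, moderate or high will correlate with the treatment outcomes of treatment response, PFS 6 and overall survival". No cut-points for the three levels are given. Section 9.2 adds "The level of blood glucose will be correlated with treatment outcome", without listing the outcomes, and remarks that "serum glucose is known to be a prognostic factor for survival in GBM".

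Section 3.3 states that "ECOG performance status and MGMT methylation which are both predictors of survival will be recorded but not used for stratification". Eligibility is broad: 4.1.4 admits ECOG 0 to 3, and 4.1.1 admits "Grade III (1p/19q intact) or Grade IV tumor".

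Section 10.5, the only statistics section, gives a 95% confidence interval for the ketosis rate and a glutamate criterion. It gives no model, covariate, test or significance level for the correlations in 9.1 and 9.2. They are also absent from the objectives in section 1.

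**The concern.** The study is single arm (3.1), so the BHB level a patient reaches reflects who that patient is as well as what the diet does. Section 9.1 itself treats BHB as one measure of compliance. The documents give reasons to think that sicker patients will find compliance harder:

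- The diet needs a daily diary (6.1.1), and measuring or weighing of food and label reading (Appendix VIII).
- ECOG 3 means limited self-care (Appendix III).
- During a hospital admission, adherence is left to the admitting physician and the patient (7.4).

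If ECOG affects both BHB and survival, it is a common cause, and the raw correlation mixes its effect with that of ketosis. The same holds for glucose, where patients who keep the diet less well would tend to have higher values. Fixing the time at which BHB is measured, for example by a landmark, would not remove this, because the confounder is present at baseline.

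The hypothesis in 1.1 is that ketosis improves outcome. PFS at 6 months and 2-year survival are otherwise compared only with historical controls. These correlations are therefore the only within-study evidence linking the level of ketosis to outcome, and a spurious gradient would be read as support.

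**Working it through.** The plan states no effect size, power or significance level for these correlations, so there is no figure of its own to reproduce. Two checks show how large the bias could be when ketosis has no effect.

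**Inputs from the protocol.** 30 patients (3.3); about half in ketosis (10.5 hopes for at least 50%); 2-year survival of 26.5% (2.1, combination arm of the cited glioblastoma trial). Expected deaths by 2 years: 30 × (1 − 0.265) = 22.05, about 22.

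**Check 1: closed form.** Assumptions, not in the documents: half the patients have good prognosis; a is the chance of ketosis in the good-prognosis group and b = 1 − a in the poor; 2-year survival is sG and sP. With no ketosis effect:

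- survival among patients in ketosis = a·sG + b·sP
- survival among the others = (1 − a)·sG + (1 − b)·sP

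| a / b | sG / sP | In ketosis | Not in ketosis | Difference | Odds ratio |
|---|---|---|---|---|---|
| 60/40% | 35/18% | 28.2% | 24.8% | 3.4 points | 1.19 |
| 70/30% | 40/13% | 31.9% | 21.1% | 10.8 points | 1.75 |
| 80/20% | 45/8% | 37.6% | 15.4% | 22.2 points | 3.31 |

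Middle row: 0.7 × 0.40 + 0.3 × 0.13 = 0.319; 0.3 × 0.40 + 0.7 × 0.13 = 0.211; odds ratio (0.319/0.681)/(0.211/0.789) = 1.75. Within either prognosis group the difference is zero, so all of the apparent gain is confounding.

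**Check 2: simulation of Cox models.** Assumptions, not in the documents: ECOG 0/1/2/3 with probabilities 0.25/0.40/0.25/0.10; exponential survival with 26.5% alive at 24 months; hazard ratio 1.5 or 2.0 per ECOG level; worse ECOG correlated with lower mean BHB at size r; no BHB effect; one-sided 2.5% Wald test for benefit; 1,500 trials per scenario in the table.

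| r | HR per ECOG level | False benefit, unadjusted | False benefit, ECOG-adjusted |
|---|---|---|---|
| 0.3 | 1.5 | 6.3% | 2.5% |
| 0.3 | 2.0 | 11.4% | 3.5% |
| 0.5 | 1.5 | 13.0% | 3.1% |
| 0.5 | 2.0 | 24.5% | 2.9% |

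The median unadjusted hazard ratio per SD of BHB runs from 0.89 to 0.75 across these rows; adjusted, it is 1.0. Repeat runs of the same design reached 27% in the worst case. At r = 0.1 to 0.2 the unadjusted rate is only about 4% to 7%, with hazard ratios of about 0.94 to 0.95 at r = 0.1.

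**Precision.** For a 15/15 split and 22 deaths, Schoenfeld's formula gives power Φ(√(22 × 0.25) × ln 2 − 1.96) = Φ(−0.33), about 37%, for a true hazard ratio of 0.5 at two-sided 5%. A false signal is therefore not small beside the chance of finding a real one.

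**The case against.** Much of the case on the other side stands.

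- **Certainty.** A reader might infer that fitter patients will make ketosis look beneficial. The documents do not support that: they give no figure for a link between ECOG and BHB, and at a weak link the distortion nearly vanishes. Caregivers may complete the diary (6.1.1), which weakens the path.
- **Section 3.3.** A reader might infer that the protocol rules out using ECOG and MGMT. It says only "which are both predictors of survival will be recorded but not used for stratification", under the number of participants. Not stratifying does not exclude covariate adjustment; the plan is silent on it.
- **MGMT and grade.** A reader might count these as confounders too. The documents give MGMT as a predictor of survival and describe GBM as the most aggressive tumour, but show no path from either to BHB.
- **Error rates.** A reader might take the simulated rates as the plan's own error rate. The plan states no test or significance level here, so they only illustrate size.
- **Adjustment as a cure.** The adjusted hazard ratio of 1.0 follows from ECOG being the only simulated confounder. Adding one unmeasured factor (assumed correlation 0.4 with BHB, hazard ratio 1.5 per SD) left ECOG-adjusted hazard ratios of 0.81 to 0.87 and 11% to 12% false benefit.
- **Stakes.** The correlations are exploratory, 9.1 hedges them, and the primary ketosis rate is unaffected.

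What remains is that the analysis is promised, exposure is not assigned, a recorded predictor of survival plausibly drives exposure, and no adjustment is specified. With 30 patients, a choice of covariates made after seeing the data could push the result either way.

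**Conclusion.** The concern holds as a risk of moderate size in an exploratory analysis. Run as written, the correlations in 9.1 and 9.2 can show a benefit of ketosis when there is none. In the simulations, false benefit is about 4% to 7% if the ECOG-BHB correlation is 0.1 to 0.2, and about 6% to 27% if it is 0.3 to 0.5, against a nominal 2.5%. These ranges rest on the assumed correlation, the assumed ECOG mix, a hazard ratio of 1.5 to 2.0 per ECOG level and 26.5% two-year survival. Only the sample size and the survival figure come from the protocol. The point should be fixed because ECOG is already collected and the remedy is cheap. It does not call the feasibility result into question.

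**What to change.** In 9.1 and 9.2, specify that:

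1. each association of BHB or glucose with survival comes from a Cox model adjusted for baseline ECOG as one ordinal covariate, with the unadjusted estimate beside it;
2. response and PFS at 6 months are shown by ECOG group, or analysed in a small or penalised logistic model if the number of events allows;
3. grade and MGMT, as predictors of outcome, are added one at a time as sensitivity analyses; for glucose, so is dexamethasone dose, which may be up to 8 mg at entry (4.1.9) and may change later (3.2.1);
4. the results are labelled exploratory and carry no causal wording.

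In 3.3, keep the statement that ECOG and MGMT are not stratification factors, and add that ECOG will be a covariate in these analyses.

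The cost is wording and about one degree of freedom. With 22 deaths and two parameters (BHB and ECOG) there are 22/2 = 11 deaths per parameter. If many Grade III patients enrol, deaths may be fewer: at an assumed 40% two-year survival, 30 × 0.60 = 18, or 9 per parameter. This is why the other covariates should enter singly. Residual confounding by unmeasured factors remains, and the report should say so.

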3. STUDY DESIGN

- 3.1. This is a single arm feasibility study.
- 3.2. Study Diet: Patients will be screened for study eligibility and written informed consent will be obtained prior to enrollment. Patients will meet with the registered dietitian (RD) one to four weeks prior to initiation of concurrent radiation and chemotherapy. At that visit, the RD will provide education on all aspects of MAD including meal planning and daily food diary completion (Appendix II). The diet will begin approximately 7 days prior to the initiation of concurrent radiation and chemotherapy and the patient will continue the study diet until the first post-radiation MRI, a time period of approximately 10 weeks. We will obtain blood to assess serum BHB, fasting insulin and glucose, and other chemistries as well as body weight weekly, according to the standard of care, while on chemotherapy and radiation therapy. Participants will receive weekly phone calls from the RD to address any questions or concerns the patient may have regarding the MAD and daily food diary. A food diary (Appendix II) will be used to assess adherence during the 10-week period. All macronutrient intake from food diaries will be entered by study agent into nutrient analysis software. This macronutrient breakdown will be utilized to identify potential problematic macronutrient intake which may be preventing patient from achieving ketosis. This is available online as well.
 - 3.2.1. Temozolomide and radiation will be given according to the standard protocol described by Stupp et al.ⁱ Patients will receive 75 mg/m² of temozolomide concurrent with radiation therapy at standard dose. The dose of radiation and/or chemotherapy and/or steroid may be modified by the attending physician based on clinical indications.
 - 3.2.2. Correlative platelet mitochondrial studies will be drawn on the pre-treatment visit #2, the post-treatment visit #1 and the post-treatment visit #2. Patients are already having blood drawn at these visits as standard of care. This sample will be transported within 6 hours to the laboratory **[name] at Cincinnati Children's Hospital Medical Center** for assessment of mitochondrial respiration in the platelets.
 - 3.2.3. QOL studies will be done at the pre-treatment visit #2, pre-treatment visit #3, weekly during chemotherapy and radiation, at the post-treatment visit #1 and then at post-treatment visit #2

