10.2. Definitions

10.2.1. **Quality of Life (QOL)**: QOL will be assessed using the FACT-Br QOL tool. See Appendix I. QOL scores pre-intervention will be compared to post intervention-QOL score. QOL will also be obtained at the post-treatment visit #2 to assess if termination of intervention decreased QOL score. We understand that there are many variables that can affect QOL during this time other than the intervention.

10.2.2. **Two-year survival (2YS)**: Duration of survival will be defined as the number of months from diagnosis to death due to any cause.

10.2.3. **6-month progression free survival (6moPFS)**: will be defined as the percentage of patients without progression (defined below) at 6 months.

10.2.4. **Ketosis**: Will be defined as serum BHB ≥ 0.5 mM

10.2.5. **Compliance**: Dietary adherence is assessed by review of the daily food diary (Appendix II) serum ketone levels.

10.3. **Methods for Evaluation of Measurable Disease**: All baseline evaluations should be performed as closely as possible to the beginning of treatment. MRI imaging techniques that can be used to determine progression are:

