10.4.1.3. Clear progression of non-measurable disease

10.4.1.4. Any new lesion

10.5 Statistics

10.5.1 Ketosis will be defined as serum BHB > 0.05 mM throughout 6-week period of radiation and chemotherapy. We hope to find that in our given sample of 30 patients at least 50% will meet this criteria. We will compute a 95% confidence interval for this rate to estimate the likely range in the target population. A 10% increase in glutamate within the tumor on the post-RT MRI as compared to the pre-RT MRI will be considered evidence that the tumor is using ketones as fuel by the conversion to glutamate.

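### Correlating on-treatment BHB and glucose with PFS6 and survival, with no landmark or adjustment, can show a modest ketosis benefit when there is none

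*Combined protocol and SAP*

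**What the plan says.** - **Planned analyses.** Section 9.1 states that "the level of serum ketosis will be correlated with treatment outcome". It calls it speculative whether the level of "ketosis as based on low, moderate or high will correlate with the treatment outcomes of treatment response, PFS 6 and overall survival", and gives no cut-points for the three levels. Section 9.2 states: "The level of blood glucose will be correlated with treatment outcome". It also notes that "serum glucose is known to be a prognostic factor for survival in GBM".
- **Ketosis definitions.** Section 10.5.1 reads: "Ketosis will be defined as serum BHB > 0.05 mM throughout 6-week period of radiation and chemotherapy". Section 10.2.4 reads: "Will be defined as serum BHB ≥ 0.5 mM". Section 10.5 gives no method for the correlations in 9.1 and 9.2: no exposure summary, model, landmark, rule for early stops, or adjustment.
- **Outcomes.** Survival runs from diagnosis (10.2.2). PFS6 is the percentage without progression at six months, with no stated time origin (10.2.3).
- **Timing of exposure.** BHB and glucose are drawn weekly over Day 0-42 and at both post-treatment visits (Schema, Appendix IV). The diet runs from about Day -7 to the first post-radiation MRI, about Day 70 (3.2, Schema).
- **What can change the exposure.** Section 3.2.1 says: "The dose of radiation and/or chemotherapy and/or steroid may be modified by the attending physician based on clinical indications". Dexamethasone is limited only at entry (4.1.9). Intercurrent illness can end treatment (6.2.1), and adherence in hospital is left to the admitting physician and the patient (7.4).
- **Covariates.** ECOG status and MGMT methylation are recorded and described as predictors of survival (3.3).

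**The concern.** The exposure is observed after the survival clock has started, and the course of the disease can change it. This creates two separate problems.

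*Guarantee time.* If a patient must show ketosis "throughout 6-week period of radiation and chemotherapy" to count as ketotic, a patient who dies or stops the diet in that window cannot clearly qualify. Such patients then drift into the low-ketosis group whatever ketosis does. Classing by values from a later visit has the same effect, more strongly.

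*Reverse causation and confounding.* A patient who is deteriorating may receive more steroid, eat differently or be admitted. Glucose then rises and BHB falls because of the disease. The protocol itself treats a raised fasting glucose as a prompt to look for medical causes such as infection (7.3).

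Both problems push towards the study hypothesis in 1.1. In a single-arm trial this is the only within-trial comparison that links ketosis to tumour outcome, so a biased result here could be read as mechanistic support.

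**Working it through.** The plan gives no effect size, error rate or method for these correlations, so there is no figure to reproduce. The check asks what a plain comparison would show if BHB had no effect.

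**1. Closed form for the 42-day rule.** Inputs: PFS6 *p* = 55% (assumed; the documents give none); ketotic share among those who complete the window *k* = 50% (the hoped-for rate in 10.5.1); *e* = share who progress before Day 42 and are counted as not ketotic (assumed).

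- Ketotic PFS6 = p / (1 - e)
- Non-ketotic PFS6 = (1 - k)p / [e + (1 - e)(1 - k)]

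For e = 10%: 0.55/0.90 = 61.1%, and 0.275/(0.10 + 0.45) = 50.0%, a gap of 11.1 points.

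| e | Ketotic | Non-ketotic | Gap (points) |
|---|---|---|---|
| 5% | 57.9% | 52.4% | 5.5 |
| 10% | 61.1% | 50.0% | 11.1 |
| 15% | 64.7% | 47.8% | 16.9 |
| 20% | 68.8% | 45.8% | 22.9 |

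To judge which *e* is plausible, count from Day 0 and take six months as 182.5 days, so 42/182.5 = 0.230. A constant hazard gives e = 1 - 0.55^0.230 = 12.9% and a gap of 63.1 - 48.7 = 14.4 points. A Weibull hazard with shape 1.5 gives e = 1 - 0.55^(0.230^1.5) = 6.4% and a gap of 58.8 - 51.7 = 7.1 points. At e = 20%, 0.20/0.45 = 44% of all six-month failures would fall in the first 23% of the period.

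**2. Null simulation.** 4,000 trials of 30 patients (N from 3.3), ketosis assigned at random to 50%, two-sided 5% log-rank test on survival. Two-year survival was set to the 26.5% quoted in 2.1. Assumed: PFS6 of 40-60%, Weibull shape 1.0 or 1.5, and patients who progress within the window counted as not ketotic. False-favourable means significant in favour of ketosis (nominal 2.5%).

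| Exposure rule | HR | False-favourable | PFS6 ketotic vs not, when true PFS6 is 50% |
|---|---|---|---|
| Independent of outcome | 1.00 | 2.5-2.9% | about 50% in both |
| Throughout 42 days | 0.81-0.93 | 3.5-6.8% | 54-59% vs 44-47% |
| Throughout 70 days | 0.71-0.86 | 4.7-11.0% | 59-65% vs 41-44% |
| Includes visit #2 (about Day 130) | 0.58-0.77 | 6.6-21.8% | 76-82% vs 36-38% |

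A mean of available draws was not simulated. Under that summary an early failure still has a value and is not moved to the low group, so the guarantee-time part should be small.

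**3. Reverse causation.** Let disease severity lower BHB (correlation 0.2-0.5) and raise the hazard (HR 1.3-2.0 per SD), with BHB itself inert. The false-favourable rate is 4.1-23.6%. Both inputs are assumed.

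**4. What a landmark does.** With exposure fixed by Day 70 and only patients alive and progression-free then, HR is 1.00-1.01 and the false-favourable rate 2.6-2.7%. A landmark does not by itself remove reverse causation. If BHB falls in the four weeks before progression, a Day 42 landmark still gives HR 0.86-0.92 and 3.6-5.3%. Day 42 plus 28 days is Day 70, so a Day 70 landmark on the Day 0-42 exposure excludes patients whose BHB was already falling under that assumption.

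**5. Glucose.** No whole-window rule exists for glucose anywhere in the documents. Steps 1 and 2 therefore do not carry over to 9.2; the mechanism there is step 3.

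**The case against.** A reader might infer that early failures fall in the low-ketosis group by construction, and that spurious gaps of 17-23 points should be expected. The documents do not support that reading.

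- The whole-window rule in 10.5.1 defines the feasibility rate that gets a confidence interval. Section 9.1 speaks of the level of ketosis, and nothing says that the correlation uses the 10.5.1 rule.
- Progression is not among the criteria in 6.2 for ending treatment. A patient who progresses can stay on the diet and keep having weekly draws.
- No MRI is scheduled between the planning scan and about Day 70. Progression before Day 42 would have to come from clinical decline or an unscheduled scan. Entry also requires a life expectancy above three months (4.1.5), which limits early deaths.
- The first scheduled response scan comes after the six-week window, so guarantee time does not fit response in the same way.
- The analysis is not listed among the objectives in section 1, sits under correlative studies, and is already called speculative for BHB.
- Evaluable is undefined in 3.3. If it meant completing six weeks, it would act as an implicit landmark.

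Most of this stands, and it limits the size of the guarantee-time part. It does not remove the problem. The exposure summary is open, and some admissible choices, including use of the scheduled visit #2 values, are clearly biased. Steroid changes and illness can act on both markers under any summary. The documents do not say that evaluable means completing the window.

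**Conclusion.** The point holds as a moderate weakness in a secondary analysis. As planned, the correlations of BHB and glucose with PFS6 and overall survival have no protection against guarantee time or reverse causation, and the likely bias favours ketosis.

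For the 42-day rule the size is HR about 0.81-0.93 and a false-favourable rate of 3.5-6.8%. At N = 30 it shows more in point estimates than in p-values. These figures assume that every patient who progresses in the window is detected and counted as not ketotic, so a less strict classification gives less bias. The 16.9 and 22.9 point gaps are arithmetically correct, but their inputs are the upper end. The reverse-causation range is wide because the documents give nothing to calibrate it.

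The ketosis rate and the other feasibility conclusions are not affected.

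**What to change.** In 9.1 and 9.2, with a matching entry in 10.5:

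1. Define exposure as each patient's mean BHB, and mean glucose, over the scheduled Day 0-42 draws. Do not use visit #2 values as exposure.
2. Analyse PFS6 and overall survival from a landmark at Day 42, among patients alive and progression-free then. State the time origin for PFS6.
3. Repeat with a Day 70 landmark as a lagged sensitivity analysis for reverse causation. It should not be the main analysis: it drops patients found progressed on the first post-radiation MRI, and exposure already closes at Day 42.
4. Report response at the Day 70 MRI separately and descriptively, since a landmark at that scan cannot serve it.
5. Show results with and without adjustment for on-treatment dexamethasone dose, baseline ECOG and MGMT, as far as 30 patients allow.
6. Label all of it hypothesis-generating.

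Two conflicts must be reconciled before any exposure groups are formed: the ketosis threshold (10.5.1 against 7.1 and 10.2.4), and the timing of post-treatment visit #2 (Schema item 8 against Appendix IV).

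The cost is SAP wording. Weekly BHB, glucose and concomitant medications are already scheduled; dexamethasone dose needs to be captured in the medication record. The downside is the loss of patients who fail before the landmark, whose number should be reported, and limited precision for adjustment.
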